11.4.3 Safety and Tolerability Assessments

Adverse Events

All AEs occurring during this clinical trial after the subject has signed the ICF document must be recorded in the Case Report Form, including the date and time of onset and outcome of each event. Events captured between Screening (Visit 1) and Visit 2 occurring prior to study product usage will be documented as baseline signs and symptoms and not AEs, unless they are "possibly," "likely," or "definitely" associated with product trial use in Screening Part I. Any AEs that are "possibly," "likely," or "definitely" associated with product trial use in Screening Part I will be listed and summarized with post-usage product-emergent AEs (PEAEs) but will be flagged with time of occurrence as Screening Part I.

All AEs will be listed. Product-emergent AEs will be summarized by product, severity, and relationship to the study product. The frequency of PEAEs (the number of PEAEs, the number of subjects experiencing a PEAE, and the percentage of subjects experiencing a PEAE) will be summarized by study group, Medical Dictionary for Regulatory Activities (MedDRA) system organ class, and preferred term. The summary and frequency PEAE tables will be presented for all causalities and for those considered related to the study product. Any severe or serious AEs will be tabulated.

Clinical Laboratory Parameters

Chemistry and hematology data will be summarized by study group. In addition, all chemistry, hematology, and urinalysis data outside the clinical reference ranges will be listed by parameter and product.

Values for any chemistry, hematology, or urinalysis parameter outside the clinical reference range will be flagged on the individual subject data listings.

Vital Signs

Vital signs data will be summarized by study group together with changes from baseline. Figures of mean vital signs along with SD bars will be presented by study group. Vital sign values outside the clinical reference range will be flagged on the individual subject data listings.

Electrocardiogram

The ECG data will be obtained directly from the 12-lead ECG trace and will include Ventricular Heart Rate, PR, QRS, QT, QT corrected using Bazett's formula (QTcB), and/or QT corrected using Fridericia's formula (QTcF) intervals.

The ECG data will be listed for each subject.

Other Assessments

All other safety assessments not detailed in this section will be listed but not summarized or statistically analyzed.

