6. STUDY DESIGN

This is a randomized, controlled, open-label, parallel group, multi-center, 5-week pilot study to determine changes in BOE in adult smokers allowed *ad libitum* use of VBM-FG2 relative to adult smokers who are not allowed use of VBM-FG2. The data collected from this study will be used to estimate the variability of differences in the percent change from Baseline to the EOS in urinary total NNAL between Test and Control Groups; these findings will be used to estimate the sample size for a future pivotal study. This study will be conducted in approximately 150 adult

smokers who are considered to be in overall good health. Subjects will be randomized (based on gender, daily cigarette consumption [<20 and 20], and quit attempts [any quit attempts/no quit attempts]) to Test (allowed VBM-FG2 use) or Control (not allowed VBM-FG2 use) product in a 3:2 ratio (90 subjects randomized to Test: 60 subjects randomized to Control) with no more than a 60:40 distribution of either males or females to either group.

Screening	Baseline Period*		Product Use Period ^t			
Visit 1	Visit 2	Visit 3	Visit 4	Visit 5	Visit 6	Visit 7
Day -28 to Day -1	Day 1	Day 8±1	Day 15 ± 1	Day 22 ± 1	Day 29± 1	Day 36 ± 1
Subject evaluated against inclusion and exclusion criteria for study eligibility	Baseline CPD data gathered using recall of previous week and daily IVRS call.		Randomization in a 3:2 ratio (Test:Control) 
 • Test = ad libitum VBM-FG2 • Control = no VBM-FG2 			
Enrollment		Randomization				

*Baseline Period = after the daily IVRS call on Day 1 through the daily IVRS call on Day 8.

^t Product Use Period = after the daily IVRS call on Day 8 through the daily IVRS call on Day 36.

Note: Subjects in both groups are allowed to smoke their regular brand cigarettes during the entire study period

Expected duration of the study, from first subject first visit through last subject last visit is approximately 3 months. Expected duration for each subject is expected to be up to approximately 5 weeks (potentially 9 weeks from Screening to EOS). All subjects will be informed that they are allowed to smoke their own cigarettes or to quit smoking during the study.

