Screening (Visit 1) will occur within 28 days of Day 1 (Day -28 to Day -1). An informed Consent Form (ICF) must be signed prior to conducting any study related procedures. Potential subjects will undergo an initial evaluation (vital signs, urine pregnancy test [females only], and questionnaires) to determine initial eligibility. If the subject passes the initial evaluation, then he/she will be provided with a sample of VBM-FG2 and asked to use the product as they like for 15 minutes. Subjects will then complete a Potential Purchase Interest Questionnaire. If they indicate that they "definitely would buy" or "probably would buy" the product on the questionnaire, then the subject will undergo the rest of the screening procedures (clinical labs and electrocardiogram [ECG]). Laboratory values will be evaluated by a local laboratory.

Subjects will return to the study site on the evening of Day 1 for Visit 2. A physical examination will be conducted and subjects who satisfy all the inclusion criteria and exclusion criteria will be eligible for enrollment in the study. Once a subject is enrolled in the study (Day 1), if they choose to no longer participate, they will be considered a drop-out/early termination subject.

During the Baseline Period, at Visits 2 and 3 (Days 1 and 8), blood and urine samples will be collected for analysis of BOE. Subjects will also complete the Past 7 Day Cigarettes Use Questionnaire while at the study site, to indicate their CPD over the previous week. During the Baseline Period (Days 1 to 8) subjects will report CPD daily through an IVRS.

At Visit 3, approximately 150 subjects will be randomized to either the Test or Control Group in a 3:2 ratio (with not more than a 60:40 distribution of either males or females to either group). VBM-FG2 will be dispensed to subjects randomized to the Test Group for *ad libitum* use beginning after the Day 8 IVRS.

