10. DEFINITION OF ANALYSIS POPULATIONS

Safety population includes subjects who have tried the test product during the study, including those subjects who participated only in the screening phase.

Intent to treat (ITT) population includes every subject who is randomized according to the randomization schedule.

Modified Intent to Treat (mITT) population includes every subject who has completed the baseline visit and has at least one post-baseline outcome measures.

Per-protocol population is defined as a subset of the ITT population, which is comprised of subjects who completed the study without any major protocol violations.

All protocol deviations that occur during the study will be considered for their severity and impact and will be taken into consideration when subjects are assigned to analysis populations. Details of subject assignment to the analysis populations will be listed.

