11.3.3 Safety Endpoints

Safety analyses will be conducted on the safety population. Safety analyses will include summaries of AEs as well as summaries of vital signs and laboratory test results.

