- Table 14.2.1-13 Frequency and Percentage of Subjects with Change from Baseline in Quitting Intentions
- Table 14.3.1-1 Summary of Product-Emergent Adverse Events
- Table 14.3.1-2 Frequency of Product-Emergent Adverse Events (All Causalities)
- Table 14.3.1-3 Frequency of Product-Emergent Adverse Events by Severity (All Causalities)
- Table 14.3.1-4 Frequency of Product-Emergent Adverse Events (Possibly, Likely, or Definitely Related to Study Product)
- Table 14.3.1-5 Frequency of Product-Emergent Adverse Events by Severity (Possibly, Likely, or Definitely Related to Study Product)
- Table 14.3.2-2 Serious Adverse Events

The TFLs that will be produced during the final analyses (all subjects) have been provided in the accompanying TFL shells document.

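### Product-related events from the pre-randomisation screening trial are pooled into the adverse-event summaries by study group, so Control can show product-related events that do not come from its assigned condition

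*SAP*

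**What the plan says.** - **Exposure before assignment.** SAP Section 6 has each person who passes the initial evaluation use the product at Visit 1: "then he/she will be provided with a sample of VBM-FG2 and asked to use the product as they like for 15 minutes". Assignment comes later: "At Visit 3, approximately 150 subjects will be randomized to either the Test or Control Group in a 3:2 ratio". The planned split is "90 subjects randomized to Test: 60 subjects randomized to Control".
- **Safety population.** Section 10: "Safety population includes subjects who have tried the test product during the study, including those subjects who participated only in the screening phase". Section 11.3.3: "Safety analyses will be conducted on the safety population".
- **Groups in the tables.** Section 7 defines two study groups, Test and Control. It names none for people who were never randomised.
- **Screening events.** Under Section 11.4.3, events between Visit 1 and Visit 2 that precede study product use count as baseline signs and symptoms unless judged at least possibly associated with the screening use. Events so judged "will be listed and summarized with post-usage product-emergent AEs (PEAEs) but will be flagged with time of occurrence as Screening Part I".
- **Summaries.** The same section gives counts and percentages of subjects with a product-emergent event by study group, first for all causalities and then for related events. Appendix 2 lists the corresponding tables, among them "Table 14.3.1-2 Frequency of Product-Emergent Adverse Events (All Causalities") and the related-event Tables 14.3.1-4 and 14.3.1-5. No listed table is limited to events after randomisation.

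**The concern.** A by-group adverse-event table should show what happened under each assigned condition. Here each column also carries events from a short exposure that all randomised subjects shared before they had a group. Three things follow from the text.

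1. Control, which is not allowed the product after randomisation, can show product-related events.
2. The all-causality tables apply two rules. Events before Visit 2 count only if related, whereas product-period events count whatever their cause.
3. Never-randomised people who tried the product belong to the population analysed but have no named group. Where their events appear, and over which denominator, is left open.

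At stake is how clearly the safety tables read, above all the related-event tables. No formal test is affected.

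**Working it through.** **Inputs from the SAP.** 150 randomised 3:2 gives 150 × 3/5 = 90 Test and 150 × 2/5 = 60 Control, which agrees with Section 6. The SAP states no adverse-event rate and no number of people who try the product without being randomised, so there is no safety figure to reproduce. Every rate below is an assumption, shown over a range.

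**Model.** Let p be the probability of a product-period event and s the probability of a related screening-trial event. Take s to be equal in both groups, because the exposure precedes randomisation, and independent of p. Then:

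- tabulated proportion = 1 − (1 − p)(1 − s) = p + s(1 − p)
- tabulated difference = (pT − pC)(1 − s)

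**All-cause events, assumed 20% Test and 10% Control, s = 4%.**

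- Test: 1 − 0.96 × 0.80 = 23.2%
- Control: 1 − 0.96 × 0.90 = 13.6%
- The difference goes from 10.0 to 9.6 points, and the ratio from 2.0 to 1.7.

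**All-cause events, assumed 30% Test and 15% Control.**

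| s | Test | Control | Difference (points) | Ratio |
|---|---|---|---|---|
| 0 | 30.0% | 15.0% | 15.0 | 2.000 |
| 2% | 31.4% | 16.7% | 14.7 | 1.880 |
| 5% | 33.5% | 19.25% | 14.25 | 1.740 |
| 10% | 37.0% | 23.5% | 13.5 | 1.574 |
| 20% | 44.0% | 32.0% | 12.0 | 1.375 |

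**Related events, assumed 15% Test and 0% Control in the product period.**

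| s | Test | Control | Control subjects of 60 | Ratio |
|---|---|---|---|---|
| 0 | 15.0% | 0% | 0 | not defined |
| 2% | 16.7% | 2% | 1.2 | 8.35 |
| 5% | 19.25% | 5% | 3 | 3.85 |
| 10% | 23.5% | 10% | 6 | 2.35 |
| 20% | 32.0% | 20% | 12 | 1.60 |

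**Denominators.** The product is tried at screening, before enrolment, so every randomised subject meets the Section 10 definition. The by-group denominators are then the group sizes, about 90 and 60. The gap concerns an overall column or the ungrouped subjects. For illustration, assume 100 screening-only people, s = 5%, and 30% and 15% as above:

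- Randomised subjects with an event: 90 × 0.335 + 60 × 0.1925 = 41.7. Over 150 this is 27.8%.
- Adding 100 × 0.05 = 5 screening-only people gives 46.7. Over a safety population of 250 this is 18.7%; over 150 it would be 31.1%.
- Product-period events only: (27 + 9)/150 = 24.0%.

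The same data would thus give overall figures from 18.7% to 31.1%, depending on a choice that the SAP does not state.

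**The case against.** Much can be said for the plan.

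- **The comparison is descriptive.** No adverse-event test is planned, the study is a pilot, and all events are listed. This stands.
- **The shared exposure favours neither group.** It adds the same expected background to both, and the risk difference hardly moves. This stands for the difference, but less so for the ratio or the related-event tables.
- **The flag may solve the problem.** A table could carry a time-of-occurrence row, and the separate table-shell document, which is not at hand, may add a column for people who were not randomised. That is possible. Even so, the SAP's own instruction is to summarise these events with the others, and it does not say how the flag would appear in a frequency table.
- **A related event in Control is not false,** because that subject did use the product at screening. True, but the column heading invites the reader to attribute it to the assigned condition.

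A reader might go further and infer that the group denominators are undefined, that screening-only events will vanish from the tables, or that the Test-versus-Control comparison is seriously distorted. The documents support none of these. The denominators for randomised subjects follow from Sections 6 and 10. Whether a column exists depends on the unseen shells. The numerical distortion rests wholly on assumed rates. However many non-randomised people try the product, the percentage in either randomised group does not change.

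**Conclusion.** The point holds as a minor but genuine defect in a stated rule. Followed as written, Section 11.4.3 places pre-randomisation product-related events in the Control column, and it admits events before Visit 2 to the all-causality tables only when they are related. The safety population includes people for whom the SAP names no group, so an overall percentage is ambiguous.

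The loss on the risk-difference scale is a factor 1 − s, or 2% to 10% of the difference for an assumed s of 2% to 10%. Over the same range, 1 to 6 of 60 Control subjects would carry a related event, where none is assumed from the product period. These sizes rest on assumed rates, equal s in both groups and independence of the two events. The structural point needs none of them.

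**What to change.** - Restrict the by-group product-emergent tables to events starting after the Visit 3 randomisation, and state that the denominator is the randomised subjects in the safety population.
- Report pre-randomisation events in a separate single-column table over everyone who tried the product at screening. It should cover both the screening-trial events and any adverse events up to Visit 3, so that those between Visit 2 and Visit 3 are not left without a table.
- State in that table that screening events are included only if judged related.
- Check that the table shells match.

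The cost is a change of wording in the SAP and one extra table. No data collection changes, and events in never-randomised people remain visible.

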12. INTERIM ANALYSES

An interim data analysis will be conducted after the first 50 subjects have completed the study. The analysis will be based on data from the 50 subjects up to the completion time point.

The purpose of the analysis is to obtain timely information for the planning of a proposed pivotal study. Therefore, no P-value adjustment will be conducted for statistical testing. Descriptive statistics (n, mean, median, SD, range, 95% CI) will be provided by study group for subject demographics, the primary endpoint variable, and the secondary endpoint variables that are continuous in scale. Frequency distribution (number and proportion) will be provided for the baseline demographics and smoking characteristics, safety variables, and the secondary endpoint variables that are categorical. The TFLs for interim analysis and final analysis (all study subjects) are presented in Appendix 2.

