APPENDIX 2: LIST OF TFLS FOR INTERIM AND FINAL ANALYSES

Following is the list of TFLs that will be produced during the interim analyses.

- Table 14.1-1 Summary of Subject Disposition
- Table 14.1-2 Summary of Screening Demographics
- Table 14.1-3 Summary of Baseline Smoking Characteristics
- Table 14.2.1-3.1 Individual Data and Summary Statistics of S-PMA
- Table 14.2.1-3.2 Individual Data and Summary Statistics of Change from Baseline S-PMA
- Table 14.2.1-3.3 Individual Data and Summary Statistics of Percent Change from Baseline S-PMA
- Table 14.2.1-4.1 Individual Data and Summary Statistics of Carboxyhemoglobin
- Table 14.2.1-4.2 Individual Data and Summary Statistics of Change from Baseline Carboxyhemoglobin
- Table 14.2.1-4.3 Individual Data and Summary Statistics of Percent Change from Baseline Carboxyhemoglobin
- Table 14.2.1-5.1 Individual Data and Summary Statistics of Exhaled Carbon Monoxide
- Table 14.2.1-5.2 Individual Data and Summary Statistics of Change from Baseline Exhaled Carbon Monoxide
- Table 14.2.1-5.3 Individual Data and Summary Statistics of Percent Change from Baseline Exhaled Carbon Monoxide
- Table 14.2.1-6.1 Individual Data and Summary Statistics of Cigarettes per Day
- Table 14.2.1-6.2 Individual Data and Summary Statistics of Change from Baseline Cigarettes per Day
- Table 14.2.1-6.3 Individual Data and Summary Statistics of Percent Change from Baseline Cigarettes per Day
- Table 14.2.1-7.1 Individual Data and Summary Statistics of Total Score of Fagerstrom Test for Cigarette Dependence
- Table 14.2.1-7.2 Individual Data and Summary Statistics of Change from Baseline Total Score of Fagerstrom Test for Cigarette Dependence
- Table 14.2.1-7.3 Individual Data and Summary Statistics of Percent Change from Baseline Total Score of Fagerstrom Test for Cigarette Dependence
- Table 14.2.1-X Individual Data and Summary Statistics of Urine Creatinine (Interim only)
- Table 14.2.1-8.1 Individual Data and Summary Statistics of VBM-FG2 Discs per Day

- Table 14.2.1-8.2 Individual Data and Summary Statistics of Change from Baseline VBM-FG2 Discs per Day
- Table 14.2.1-8.3 Individual Data and Summary Statistics of Percent Change from Baseline VBM-FG2 Discs per Day
- Listing 16.2.8-12 Other Tobacco or Nicotine Containing Product Use Questionnaire by Subject
- Table 14.2.1-12 Individual Data and Summary Statistics for Number of Quit Attempts with Change from Baseline

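### As worded, the interim analysis covers only the first 50 completers, so its disposition and adverse event tables leave out subjects who withdrew

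*SAP*

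**What the plan says.** Section 12 of the SAP sets the trigger: "An interim data analysis will be conducted after the first 50 subjects have completed the study". The next sentence sets the data: "The analysis will be based on data from the 50 subjects up to the completion time point". No other subjects are added. The aim follows: "The purpose of the analysis is to obtain timely information for the planning of a proposed pivotal study". The content includes safety: "Frequency distribution (number and proportion) will be provided for the baseline demographics and smoking characteristics, safety variables, and the secondary endpoint variables that are categorical".

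Appendix 2 names the interim outputs. They include "Table 14.1-1 Summary of Subject Disposition", five tables of product-emergent adverse events (14.3.1-1 to 14.3.1-5) and "Table 14.3.2-2 Serious Adverse Events".

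On people who leave after enrolment, Section 6 says: "if they choose to no longer participate, they will be considered a drop-out/early termination subject". Section 10 uses completion of the study as a dividing line in the Per-protocol definition: "comprised of subjects who completed the study without any major protocol violations". The same section defines the safety population as anyone who tried the product, including people seen only at screening. Section 11.3.3 assigns the safety analyses to that population and makes no exception for the interim.

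**The concern.** A subject who started in the same weeks as the 50 completers but withdrew falls outside the interim as Section 12 is written. Two listed outputs suffer directly. A disposition table restricted to completers reports full completion whatever happened in the study. The AE/SAE tables cannot contain any event that led someone to leave, nor any other event in a person who left.

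This is an open-label study in which only the Test Group receives product after randomisation, so withdrawal for dislike or intolerance could differ by arm. A reader of the interim tables who plans the pivotal study would see nothing of it. The data need not be lost: Section 6 allows the end-of-study visit to take place at early termination, so information on withdrawn subjects can be collected and would simply go unused at this look.

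**Working it through.** **Step 1. The plan's own size figure.** Section 6 plans about 150 subjects at 3:2. 150 × 3/5 = 90 Test and 150 × 2/5 = 60 Control, as stated. The SAP gives no drop-out rate, SD or effect size, so nothing else can be reproduced.

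**Step 2. Who is in the interim.**

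| Place in SAP | What it implies |
|---|---|
| Section 12 | 50 subjects who completed; only their data |
| Section 6 | Those who leave after enrolment are drop-outs/early terminations |
| Section 10, safety population | All product triers, including screening-only subjects |
| Section 11.3.3 | Safety analyses use the safety population |
| Section 10, mITT | Baseline visit plus one post-baseline measure; completion not needed |
| Section 11.4.1 | Primary models on mITT and Per-protocol |
| Section 11.4.2 | Secondary analyses on Per-protocol only |

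The first two rows together give a completers-only set. Rows three and four cannot be met by that set, because it contains neither withdrawn nor screening-only subjects. The last three rows show that the contrast with mITT applies to the primary endpoint only; secondary endpoints are restricted to Per-protocol at the final analysis as well.

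**Step 3. How many are left out.** With an assumed drop-out proportion d, the number randomised who correspond to 50 completers is N = 50/(1 − d), rounded up.

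| Assumed d | 50/(1 − d) | N | Left out (N − 50) |
|---|---|---|---|
| 5% | 52.6 | 53 | 3 |
| 10% | 55.6 | 56 | 6 |
| 15% | 58.8 | 59 | 9 |
| 20% | 62.5 | 63 | 13 |

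If completion is equal by arm, the 50 completers split into 50 × 3/5 = 30 Test and 50 × 2/5 = 20 Control. Those are completers; the Test subjects who started would number more.

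**Step 4. Effect on an adverse event percentage (illustration).** Assume 20% of completers have an event. If 50% to 100% of withdrawn subjects have one, then:

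- at d = 10%, the rate in everyone is (50 × 0.20 + 6 × 0.50)/56 = 23% to (50 × 0.20 + 6 × 1.00)/56 = 29%;
- at d = 20%, it is (50 × 0.20 + 13 × 0.50)/63 = 26% to (50 × 0.20 + 13 × 1.00)/63 = 37%.

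The completers-only table would show 20% in each case.

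**Step 5. Effect on variability (illustration).** Assume a completer mean change of −20 points with SD 40, and withdrawn subjects worse by a gap g with the same SD. In the mixture, mean = −20 + d·g and SD = √(40² + d(1 − d)g²).

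- d = 10%, g = 10: mean −19, SD = √(1600 + 9) = 40.1.
- d = 20%, g = 20: mean −16, SD = √(1600 + 64) = 40.8.

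The SD hardly moves. The mean does, but only because a gap was assumed.

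**The case against.** The strongest reply is that completer is not a defined term and that other parts of the SAP point away from a completers-only intent. Section 11.3.3 puts safety on the safety population without exception, and if it governs the interim AE tables, those tables are complete. Section 6 lets the end-of-study visit be an early termination visit. A disposition table has little use at an interim that cannot show a withdrawal. These points make the intent uncertain, but they do not remove the defect: Section 12 limits the data to the 50 in so many words and nothing says which section prevails.

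A reader might also infer that withdrawals are lost from the pivotal planning altogether, or that the sample size for that study will be biased. The documents do not support this. Sections 6 and 8 use the pilot as a whole for sizing. The final analysis covers all subjects, with mITT among the primary-model populations and the safety population for safety. The planning input that the SAP names is variability of the primary outcome, and no distortion of it is shown; in the illustration the SD barely changes. Nor does the SAP say that the interim is meant to estimate a drop-out rate, and the sponsor can count enrolments outside the tables.

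Finally, no stopping or go/no-go rule for this trial is tied to the interim, and it is mainly descriptive. That stands, and it limits the weight of the point.

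**Conclusion.** The point holds for the interim look only. On its plain wording, Section 12 yields a disposition table without withdrawals and six AE/SAE tables without the events of those who withdrew, in conflict with Sections 10 and 11.3.3. Events in subjects who stopped using the product but stayed to Visit 7 would still appear; what is missing is everything from those who left the study.

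The size is illustrative: about 3 to 13 randomised subjects beside the 50 completers, resting on an assumed drop-out of 5% to 20%. The size and direction of any shift in adverse event rates or mean effect cannot be derived from the SAP. The wording is worth correcting before the interim is run, because it changes what those tables show. It is no threat to the final analysis.

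**What to change.** In Section 12, keep the 50-completer trigger and add a definition of the interim cohort: all randomised subjects whose scheduled Visit 7 date, with its window (Day 36 + 1), has passed at the data cut, whether they completed or withdrew, with their data up to the cut. Use this cohort for the disposition, product-use and endpoint tables, and apply the mITT rule to the primary endpoint. State whether the Per-protocol restriction of Section 11.4.2 applies to the interim tables of secondary endpoints.

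For the AE/SAE tables, use the safety population at the cut, as Section 11.3.3 requires, or at least all product-exposed subjects in the cohort, and state which.

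The cost is a wording change and more records to clean before the interim; no visits or subjects are added. With the cohort option, the extra records are those of the withdrawn subjects (about 3 to 13 under the assumption above). With the full safety population the load is larger, because subjects sample the product at screening: people never enrolled and all ongoing subjects would come in. That works against the wish for timely information, so the choice should be made openly.
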